5.2.4.2 Continuous ECG monitoring

Cardiac rhythm (including heart rate) will be monitored during the SRD part by means of continuous 3-lead ECG recording for at least 15 min before (for baseline assessment) and 6 h following drug administration using patient monitors (e.g. Carescape B450, GE Healthcare GmbH, Freiburg, Germany). Abnormal findings will be recorded as AEs if judged clinically relevant by the Investigator but no other data will be transferred to the database.

5.2.5 Assessment of other safety parameters

5.2.5.1 Vital signs

Systolic and diastolic blood pressures (BP) as well as pulse rate (PR) will be measured by a blood pressure monitor (Dinamap Pro 100, GE Medical Systems, Freiburg, Germany) at the times indicated in the [Flow Chart](#), after subjects have rested for at least 5 min in a supine position. All recordings should be made using the same type of blood pressure recording instrument on the same arm if possible.

5.2.5.2 Medical examinations

At screening, the medical examination will include demographics including height and body weight, smoking and alcohol history, relevant medical history and concomitant therapy, review of inclusion and exclusion criteria, review of vital signs (BP, PR), 12-lead ECG (including rhythm strip of at least 15 minutes), laboratory tests, and a physical examination. At the end of trial examination, it will include review of vital signs, 12-lead ECG, laboratory tests, and a physical examination.

5.3 OTHER

5.3.1 Pharmacogenomic evaluation

Pharmacogenomic investigations explore the role of genetic variation in determining an individual's response to drugs. For this purpose, a sample of at most 10 mL of blood will be taken at the screening examination from each subject whose genotype has not been previously determined. Separate informed consent for genotyping will be obtained from each volunteer prior to sampling.

DNA will be extracted from the blood sample in order to sequence genes coding for proteins that are involved in the absorption, distribution, metabolism, and excretion (ADME) of drugs. The gene sequences to be determined include known and likely functional variations of key ADME genes and incorporate more than 90% of ADME-related genetic markers identified by the PharmaADME group ([weblink.pharmaadme.org](#)). It is not intended to include the pharmacogenomic data in the final report. However, the data may be part of the report if necessary.

5.4 APPROPRIATENESS OF MEASUREMENTS

All measurements performed during this trial are standard measurements and will be performed in order to monitor subjects' safety and to determine pharmacokinetic parameters and biomarkers in an appropriate way. The scheduled measurements will allow monitoring of changes in vital signs, standard laboratory values, and ECG parameters that might occur as a result of administration of trial medication. The safety assessments are standard, are accepted for evaluation of safety and tolerability of an orally administered drug, and are widely used in clinical trials. The pharmacokinetic parameters and measurements outlined in Section 5.5 are generally used assessments of drug exposure. The biomarkers and measurements outlined in Section [5.6](#) are of exploratory nature only.

5.5 DRUG CONCENTRATION MEASUREMENTS AND PHARMACOKINETICS

Exact time points of plasma sampling will be derived from the study management system ClinBase™ and documented in the CRFs by the medical personnel or sent as electronic files to the trial data manager. The actual sampling times will be used for determination of pharmacokinetic parameters.

PK sampling times and periods may be adapted during the trial based on information obtained during trial conduct (e.g. preliminary PK data) including addition of samples and visits as long as the total blood volume taken per subject does not exceed 500 mL. Such changes would be implemented via non-substantial CTP Amendments.

5.5.1 Pharmacokinetic endpoints

The following pharmacokinetic endpoints will be determined if feasible:

5.5.1.1 Secondary endpoints

- $AUC_{0-\infty}$ (area under the concentration-time curve of the analyte in plasma over the time interval from 0 extrapolated to infinity)
- C_{\max} (maximum measured concentration of the analyte in plasma)

5.5.2 Methods of sample collection

5.5.2.1 Plasma sampling for pharmacokinetic analysis

For quantification of BI 730357 plasma concentrations, 2.7 mL of blood will be taken from an antecubital or forearm vein into an K₃-EDTA (tripotassium ethylenediaminetetraacetic acid)-anticoagulant blood drawing tube at the times indicated in the [Flow Chart](#). Blood will be withdrawn by means of either an indwelling venous catheter or by venipuncture with a metal needle.

The EDTA-anticoagulated blood samples will be centrifuged for about 10 min at about 2000 g to 4000 g and at 4 to 8 °C. Two plasma aliquots will be obtained and stored in polypropylene tubes. The first aliquot should contain at least 0.5 mL plasma. The process from blood collection until transfer of plasma aliquots into the freezer should be completed within 90 min, with interim storage of blood samples on crashed ice between blood collection and centrifugation. For each aliquot the time when the sample was placed in the freezer will be documented. Until transfer on dry ice to the analytical laboratory, the aliquots will be stored upright at about -20°C or below at the trial site. The second aliquot will be transferred to the analytical laboratory after the bioanalyst has acknowledged safe arrival of the first aliquot. At the analytical laboratory the plasma samples will be stored at about -20°C or below until analysis.

At a minimum, the sample tube labels should list the following information: BI trial number, subject number, visit, and planned sampling time. Further information such as matrix and analyte may also be provided.

After completion of the trial the plasma samples may be used for further methodological investigations, e.g. for stability testing, assessment of metabolites. However, only data related to the analyte and/or its metabolite(s) including anti-drug antibodies (if applicable) will be generated by these additional investigations. The study samples will be discarded after completion of the additional investigations but not later than 5 years upon the final study report has been signed.

Proprietary confidential information © 2017 Boehringer Ingelheim International GmbH or one or more of its affiliated companies

5.5.2.2 Plasma sampling for metabolism analysis

Additional K₃-EDTA plasma samples for the identification of drug metabolites will be investigated in the 25 mg dose group. Based on the knowledge gained during the trial conduct, e.g. from preliminary PK results, the dose group may be changed. The change will be implemented via a non-substantial CTP Amendment.

The blood samples will be drawn in parallel to PK samples on Days 1 to 5 of the SRD part (see [Flow Chart](#)). At each of these time points, 2.7 ml blood will be needed for metabolite analysis. Apart from the storage temperature (see below) the blood samples will be processed in the same way as the PK samples described in Section [5.5.2.1](#).

Two plasma aliquots will be obtained and stored in polypropylene cryotubes. The first aliquot (labelled as MIST-1 samples), should contain at least 0.5 mL of plasma. The remaining plasma will be the second aliquot (labelled as MIST-2 samples). The process from blood collection to the transfer of plasma aliquots into the freezer should be completed within 90 min, with interim storage of blood samples on crashed ice between blood collection and centrifugation. Until transfer on dry ice to the metabolism laboratory, the aliquots will be stored at the trial site. Samples will be positioned upright and will be frozen at approximately -70°C. The second aliquot will be shipped to the metabolism laboratory after the metabolism scientist has acknowledged safe arrival of the first aliquot. At the metabolism laboratory, the plasma samples will be stored at about -70°C until analysis.

At a minimum, the sample tube labels should list the following information: BI trial number, subject number, visit, planned sampling time and 'MIST-1 or 'MIST-2'. Further information such as matrix and analyte may also be provided.

Plasma samples dedicated to metabolism investigation are transferred to:

Department of Drug Metabolism & Pharmacokinetics
Boehringer Ingelheim Pharmaceuticals, Inc
Pharmaceuticals, Inc.
[name]
[name]
[name].
Phone: [REDACTED]

Only data related to the parent compound and its metabolites will be acquired. Evaluation of the drug metabolism will be reported separately but not included in the CTR of this trial. The study samples will be discarded after completion of the experiments but not later than 5 years after the final study report has been signed.

5.5.3 Analytical determinations

5.5.3.1 Analytical determination of analyte plasma concentration

BI 730357 concentrations in plasma will be determined by a validated LC-MS/MS (liquid chromatography tandem mass spectrometry) assay. All details of the analytical method will be available prior to the start of sample analysis.

As described in Section [4.1.5](#), the bioanalyst will be blinded for the BA part only. For the SRD part he/she will be unblinded.

5.7

PHARMACOKINETIC - PHARMACODYNAMIC RELATIONSHIP

6. INVESTIGATIONAL PLAN

6.1 VISIT SCHEDULE

Exact times of measurements outside the permitted time windows will be documented. The acceptable time windows for screening and end of trial examination are given in the [Flow Chart](#).

Study measurements and assessments scheduled to occur 'before' trial medication administration on Day 1 are to be performed and completed within a 3 h-period prior to the trial drug administration (including blank values for PK and biomarkers).

Starting from 72 h post administration a deviation from the scheduled time for PK and biomarker sampling of ± 70 min is acceptable.

The acceptable deviation from the scheduled time for vital signs, ECG and laboratory tests will be ± 15 min for the first 6 h after trial drug administration and ± 30 min thereafter.

Starting from 72 h post administration a deviation from the scheduled time for vital signs, ECG and laboratory tests of ± 70 min is acceptable.

If scheduled in the Flow Chart at the same time as a meal, blood sampling, vital signs and 12-lead ECG recordings have to be done first. Furthermore, if several measurements including venipuncture are scheduled for the same time, venipuncture should be the last of the measurements due to its inconvenience to the subject and possible influence on physiological parameters.

For planned individual plasma concentration sampling times and urine collection intervals refer to the Flow Chart. While these nominal times should be adhered to as closely as possible, the actual sampling times will be recorded and used for determination of pharmacokinetic parameter.

If a subject misses an appointment, it will be rescheduled if possible. The relevance of measurements outside the permitted time windows will be assessed no later than at the Blinded Report Planning Meeting.

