4.1.5 Blinding and procedures for unblinding

4.1.5.1 Blinding

In the present trial, treatments of the SRD part will be blinded to subjects only. With the rising dose design, single-blind conditions regarding the subjects' treatment (active or placebo) are maintained within each dose group, however the current dose level will be known to subjects and Investigators. Treatments of the BA part will be open-label.

The database of this trial will be handled open-label, because no bias with regard to data cleaning of safety measures is expected. This is considered acceptable because the potential for bias seems to be low and does not outweigh practical considerations. The bioanalyst will be blinded for the BA part only.

The bioanalyst of analytical laboratory and the trial pharmacokineticist may receive the randomisation codes of the SRD part prior to official unblinding to perform the preliminary PK analysis. He or she will treat the codes confidentially.

In addition, the drug metabolism scientist may receive the randomisation codes prior to official unblinding to perform metabolites in safety testing analysis (MIST). He or she will confirm in writing that the codes will be treated confidentially.

Within the ECG laboratory, the staff involved with interval measurements and assessments will be blinded with respect to the treatment within each dose level and also with regard to the recording date and time as well as time the points of the ECGs. The interval measurements for a given subject will be performed in a random and blinded sequence by a single technician. No more than two different blinded readers will evaluate the ECGs of the study.

Proprietary confidential information © 2017 Boehringer Ingelheim International GmbH or one or more of its affiliated companies

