7.3.4 Preliminary PK analyses

A preliminary analysis of PK parameters (AUC_{0-24} and C_{max} of BI 730357) provided as individual values and geometric means of at least the first cohort per dose level, will be performed for

- all dose levels up to n-2 before proceeding to dose level n (with $n \leq 50$ mg)
- all dose levels up to n-1 before proceeding to dose level n (with $n > 50$ mg)

(Note: Data from the first cohorts of the above mentioned dose levels will be sufficient as long as the data from at least 2 subjects on active were available)

A preliminary analysis of pharmacodynamic biomarkers is not planned.

In contrast to the final PK/PD calculations, the preliminary analysis will be based on planned sampling times rather than on actual times, regardless of whether actual times were within the time windows or not. Therefore, minor deviations of preliminary and final results may occur. The preliminary analysis will provide individual and mean concentration/effect-time profiles and summary statistics of individual values without subject identification. The preliminary results will be distributed to the Investigator and the trial team.

Depending on preliminary data on safety, tolerability, changes of dosing schedule (e.g. additional intermediate doses) or planned times for PK/biomarker-sampling, additional preliminary PK-analysis may be performed based on the request of the trial clinical monitor, the Investigator, or trial clinical pharmacokineticist. Preliminary PK data will be distributed to the Investigator. No formal interim report will be written.

No inferential statistical preliminary analysis is planned. However, after each dose group the Investigator (or [redacted] deputy) is allowed to postpone further dose progression until a preliminary analysis of the data already obtained has been performed.

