6.2 IMPORTANT PROTOCOL VIOLATIONS

Data discrepancies and deviations from the CTP will be identified for all randomised subjects. Listings of protocol deviations and of unresolved discrepancies will be provided to be discussed at the combined report planning and database lock meeting (RPM/DBLM), e.g. deviations in drug administration, in blood sampling etc. At this meeting, it will be decided whether the discrepant data can be used as they are or whether the data have to be corrected in the clinical database.

Each protocol deviation must be assessed to determine whether it is an important protocol violation. A protocol violation (PV) is important if it affects the rights or safety of the study subjects or if it can potentially influence the primary outcome measure(s) for the respective subjects in a way that is neither negligible nor in accordance with the study objectives. This last category of important PV forms the basis for the decision of whether a subject does or does not belong to an analysis set. PVs that do not influence the subject's rights and safety or the evaluability of the subjects for the main study objectives are called non-important PVs. These are only considered when checking the trial quality in general.

If any important PVs are identified, they are to be summarised into categories and will be captured in the RPM/DBLM minutes via an accompanying Excel spreadsheet [001-MCS-50-413_RD-02] (2). The following table contains the categories which are considered to be important PVs in this trial. If the data show other important PVs, this table will be supplemented accordingly by the time of the RPM/DBLM.

Table 6.2: 1 Important protocol violations

Category /Code	Description
A	Entrance criteria not met
A1	Inclusion criteria violated
A2	Exclusion criteria violated
B	Informed consent
B1	Informed consent not available
B2	Informed consent too late
C	Trial medication and randomisation
C1	Incorrect trial medication taken
C2	Randomisation not followed
C3	Non-compliance
C4	Incorrect intake of trial medication
C5	Improper washout between treatments
D	Concomitant medication
D1	Prohibited medication use
D2	Mandatory medication not taken
D3	Improper washout of concomitant medication
E	Missing data
E1	Certain violations of procedures used to measure secondary data
F	Incorrect timing¹
F1	Certain violations of time schedule used to measure secondary data
G	Other trial specific important violations

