6.3 SUBJECT SETS ANALYSED

- Randomised set (RS):
This subject set includes all randomised subjects, whether treated or not.
- Treated set (TS):
This subject set includes all subjects from the RS who were dispensed study medication and were documented to have taken at least one dose of investigational treatment.
This is the full analysis set population in the sense of ICH-E9 ([1](#)). It is used for safety analysis.

CTP: *Pharmacokinetic parameters of a subject will be included in the analysis unless the subject has an important protocol violation relevant for the evaluation. Whether a protocol violation is important will be decided no later than in the Report Planning Meeting.*

Reasons for exclusion of single pharmacokinetic parameters may be:

- *The subject experiences emesis at or before two times median t_{max} . Median t_{max} is to be determined for the test product excluding the subjects experiencing emesis.*
- *The subject experiences emesis at any time during the labelled dosing interval.*
- *Time deviations*
- *Use of restricted medications*

The subject set for the evaluation of PK endpoints (PKS) will include all treated subjects that provide at least one observation for at least one secondary endpoint without important protocol violations with respect to the statistical evaluation of PK endpoints. It will also be decided in the Report Planning Meeting which subjects are to be included in the PKS.

Excluded subjects will be listed with their individual plasma concentrations and individual pharmacokinetic parameters, however, will not be included in descriptive statistics for plasma concentrations, pharmacokinetic parameters or other statistical assessment.

- PK parameter analysis set (PKS):
This subject set includes all evaluable subjects from the TS of the SRD part or BA part who were treated with BI 730357 and who provide at least one secondary PK endpoint ($AUC_{0-\infty}$ or C_{max}) that was not excluded according to the description above.

[figure not shown]
In the SRD part, it is used for assessment of dose proportionality under fasting conditions and for intra-individual comparison of fed conditions
In the BA part, it is used for assessment of the bioavailability and food effect.
- Pharmacodynamic set (PDS):

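### The Blinded Report Planning Meeting in Protocol 6.1 is a safeguard the design does not provide, so judgement-based PK exclusions can be made with treatment, and for some staff exposure, known

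*Protocol*

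**What the plan says.** **The meeting.** Protocol 6.1: "The relevance of measurements outside the permitted time windows will be assessed no later than at the Blinded Report Planning Meeting". Protocol 7.3.2 and SAP 6.3 give the choice of PK set (PKS) to a Report Planning Meeting without calling it blinded: "It will also be decided in the Report Planning Meeting which subjects are to be included in the PKS". Under SAP 6.2, protocol deviations are listed "to be discussed at the combined report planning and database lock meeting", again with no reference to blinding.

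**Who is blinded.** Protocol 4.1.5.1 says that "treatments of the SRD part will be blinded to subjects only" and that the BA part is open-label. On the data: "The database of this trial will be handled open-label, because no bias with regard to data cleaning of safety measures is expected". The next sentence adds a general reason, that the potential for bias seems low. On the assay: "The bioanalyst will be blinded for the BA part only". ECG laboratory readers are blinded separately. Protocol 4.1.5.2 says treatment information will be known.

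**Who sees PK.** Besides the bioanalyst, "the trial pharmacokineticist may receive the randomisation codes of the SRD part prior to official unblinding to perform the preliminary PK analysis". Protocol 7.3.4: "The preliminary results will be distributed to the Investigator and the trial team". The same section says these results carry no subject identification.

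**What is left to judgement.** Protocol 7.3.2 lists emesis, time deviations and restricted medications as reasons that may lead to exclusion of a PK parameter. Protocol 7.3.5 leaves exclusion of concentrations to case-by-case decision. SAP 6.2 lets the table of important violations be extended up to the meeting.

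**The concern.** The word Blinded tells a reader that at least some data-handling decisions are taken without knowledge of treatment or results. Nothing else in the plan creates that condition.

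For PK exclusions, the blind that matters is to concentrations. The PKS contains only subjects given BI 730357, the dose level is known to investigators, and in DG 8 and 9 the visit identifies the diet. Knowing the treatment code therefore adds little; knowing that a subject's exposure is unusually high or low adds a lot.

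If a borderline time deviation or concomitant medication is judged with that value in view, an outlying subject can be excluded partly because of the value. The estimate then shifts and its interval narrows. The analyses exposed to this are the dose-proportionality slope, the DG 8/9 diet ratio and the two BA ratios.

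**Working it through.** **1. Texts side by side**

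| Question | Protocol 6.1 | Elsewhere |
|---|---|---|
| Is the meeting blinded? | Yes, by its name | Not stated in Protocol 7.3.2, SAP 6.2 or SAP 6.3 |
| Is treatment hidden from staff? | Implied | No (Protocol 4.1.5.1, 4.1.5.2) |
| Is the database blinded? | Implied | No (Protocol 4.1.5.1) |
| Are PK values hidden? | Not stated | Pharmacokineticist may hold SRD codes; team receives de-identified preliminary results |

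Some PK results must also exist when exclusions are settled. The emesis rule uses the observed median tmax, and SAP 6.3 requires a usable AUC0-∞ or Cmax for the PKS. The amendment 3 rationale (05 May 2017) already quotes 400 mg exposures and a 36% fed/fasted increase; the SAP is dated 22 September 2017.

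Two SAP details leave the PK decision without a test of its own. The data-related criterion for an important violation in SAP 6.2 is influence on the primary outcome, which here is adverse reactions. The footnote to SAP Table 6.2: 1 calls a time deviation important only when it leads to exclusion of the entire subject, while importance is what decides set membership.

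**2. Effect of one exclusion**

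The plan gives no figure for this. The variabilities below are assumptions: 20–30% is the intra-subject range in Protocol Table 7.6: 1, and 40% and 60% for the slope are illustrative.

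Log-scale SD: σ = √ln(1+CV²), giving 0.198 (20%), 0.294 (30%), 0.385 (40%) and 0.555 (60%).

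As a check, N=12, gCV 20% and 20 df give 1.725 × 0.198 × √(2/12) × √(31.41/20) = 0.175. This is the log-scale half-width in Protocol Table 7.6: 1, with interval 83.97–119.10 at a ratio of 100.

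*Paired ratios.* The SD of a within-subject difference is √2·σ. Removing one of n subjects lying z SD from the mean shifts the log ratio by z·√2·σ/(n−1). Period adjustment is ignored.

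| Estimate | gCV | z=1 | z=2 |
|---|---|---|---|
| DG 8/9, n=6 | 20% | 0.280/5 = 0.056 → 5.8% | 0.112 → 11.9% |
| DG 8/9, n=6 | 30% | 0.415/5 = 0.083 → 8.7% | 0.166 → 18.1% |
| BA, n=12 | 20% | 0.280/11 = 0.025 → 2.6% | 0.051 → 5.2% |
| BA, n=12 | 30% | 0.415/11 = 0.038 → 3.8% | 0.075 → 7.8% |

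A simulation that always drops the most extreme subject gives median shifts of 8.3–12.5% (n=6) and 4.7–7.1% (n=12) over the same gCV range.

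The BA shifts compare with planned log half-widths of 0.175 (20%) and 0.259 (30%).

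*Slope.* SAP 7.5.2 uses five fasted tablet doses (25, 50, 100, 200, 400 mg) with 6 active subjects each. In ln dose, Sxx = 6 × 10 × (ln 2)² = 28.83. The top dose lies 2·ln 2 = 1.386 above the mean, with leverage 1/30 + 1.386²/28.83 = 0.10. Dropping one subject there with residual zσ shifts the slope by 1.386·zσ/(28.83 × 0.90).

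- CV 40%: 0.021 (z=1) to 0.041 (z=2); 95% CI half-width 2.048 × 0.385/√28.83 = 0.147.
- CV 60%: 0.030 to 0.059; half-width 0.212.

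**The case against.** The strongest reply is that Blinded is a leftover word. It qualifies the meeting only in Protocol 6.1, which concerns out-of-window measurements; the sections that govern the PKS never promise blinding, and Protocol 4.1.5 is candid that treatment is known. This is plausible, and it limits the contradiction to one sentence. But deleting the word leaves the discretionary PK exclusions with no stated safeguard.

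Other points narrow the concern and stand:

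- Actual sampling times are used for PK parameters, and the SAP section 7 text on concentration exclusions keeps time-deviating values usable for analyses based on actual times. Few time deviations should need exclusion.
- The rule for predose values above 5% of Cmax is fixed, and violation categories are listed in advance.
- Excluded subjects are listed with their values, and exclusions are flagged with a comment. That makes selective dropping visible, but does not show how the ratio changed.
- Detailed rules sit in sponsor procedures that are not available here, so how much judgement remains is unknown.
- The BA bioanalyst is blinded, and Protocol 4.1.5.1 gives a general low-bias reason as well as the one on safety data cleaning.

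A reader might infer that the whole trial team decides exclusions while holding each subject's exposure. The documents do not support this: shared preliminary PK is without subject identification, and its named parameters are AUC0-24 and Cmax from at least the first cohort, not AUC0-∞. Identifiable exposure before the final analysis is clear only for those given the codes.

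**Conclusion.** The inconsistency is real: Protocol 6.1 names a safeguard that Protocol 4.1.5 and SAP 6.2 do not provide, and some PK exclusions are discretionary. The consequence is modest. Under the assumed variabilities, one discretionary exclusion moves the DG 8/9 diet ratio by about 6–18%, a BA ratio by about 3–8%, and the slope by about 0.02–0.04 at CV 40%. The BA and slope shifts lie well inside the corresponding intervals; the diet ratio, with six subjects, is the most exposed.

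A reader might apply the shift in a single dose group's geometric mean (zσ/5, or 12–25% at an assumed CV of 60%) to all these results. None of the named estimates is a single-group mean, so that overstates the case. Nor do the documents show that any exclusion was made because of its value.

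All affected endpoints are secondary, with estimation only and no acceptance range (Protocol 7.2). The primary safety endpoint uses the Treated Set and is untouched. The point is worth correcting because the correction is cheap; it does not threaten the trial's main conclusion.

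**What to change.** In Protocol 6.1 and 7.3.2 and SAP 6.2 and 6.3:

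1. Delete Blinded, or state who is blinded to what at the meeting.
2. Decide discretionary exclusions for time deviations and restricted medications from deviation listings that show no concentrations or PK parameters, and sign them before PK values are shown. Treatment or diet may appear where the judgement needs it, for example categories C1 (incorrect medication) and G1 (incorrect meal).
3. Then apply the rules that depend on treatment, evaluability or PK: PKS evaluability, predose above 5% of Cmax, and emesis relative to tmax. A PKS decision made wholly without codes and PK values is not workable, because SAP 6.3 requires BI 730357 treatment and a usable AUC0-∞ or Cmax.
4. For any discretionary exclusion made with PK values known, including case-by-case concentrations and late-added violation categories, report the affected slope or ratio with and without the subject.

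The cost is one extra listing format and a small sensitivity display, with no new data. People who have already seen PK results cannot be re-blinded, which is why step 4 is needed.
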